## **1. OBJECTIVES**

### **1.1 Study Design**

The study is a phase II study to evaluate vaccination with DC/myeloma fusions/GM-CSF and nivolumab in patients diagnosed with relapsed multiple myeloma previously treated with a proteasome inhibitor, IMiD, and anti-CD38 mAb therapy. Patients meeting initial eligibility will be enrolled and vaccine production will be initiated via the harvesting of autologous tumor cells and generation of DCs from adherent mononuclear cells. During the period of vaccine generation, patients will undergo therapy with 1-2 cycles of standard of care therapy. Patients without disease progression will then undergo monthly vaccination with DC/MM fusions for cycles 1, 2, and 3 in conjunction with nivolumab administered on day 1 and 15 and will then receive nivolumab alone for 3 additional cycles, for a total of 6 cycles of treatment.

### **1.2 Primary Objectives**

#### **1.2.1 Primary Immunologic Endpoint**

The primary endpoint is to define the immunologic response to nivolumab and the DC/MM fusion vaccine with respect to the induction of myeloma-specific immunity in patients with relapsed disease after prior proteasome inhibitor, IMiD, and anti-CD38 mAb therapy. Specifically, we will quantify the expansion of treatment-induced myeloma-specific T cells in the circulation as measured by pre-therapy and peak post-treatment levels of CD4 and CD8 T cells expressing IFN $\gamma$  following ex-vivo exposure to autologous tumor lysate. The percentage of patients achieving at least a 3 and 10-fold expansion of myeloma-specific T cells will be determined.

### **1.3 Secondary Objectives**

#### **1.3.1 Secondary Immunologic Endpoints**

We will determine the effect of therapy on the percent of marrow-infiltrating myeloma-specific T cells as measured by pre-therapy and peak post-treatment levels of CD4 and CD8 T cells expressing IFN $\gamma$  following ex vivo exposure to autologous tumor lysate. We will also quantify T cells specific to shared myeloma antigens potentially including MUC1, NY-ESO, PRAME, Survivin, XPB-1, SOX2, and WT1 by pentamer analysis. Assessment of the immune landscape will consist of quantifying T cell subsets in the circulation and marrow, presence of MDSCs, PD-1 expressing T cells, Tregs, and immunoregulatory microRNAs and will be correlated with immunologic response.

#### **1.3.2 Secondary Clinical Endpoints**

To determine the clinical response and safety of nivolumab and the DC/MM fusion vaccine in patients with relapsed disease. The percentage of patients achieving complete, very good partial and partial response will be quantified. Minimal residual disease (MRD) status will be determined. Progression free survival (PFS) will be assessed.

## **2. BACKGROUND**

### **2.1 Therapeutic approaches in Multiple Myeloma**

Despite major recent advances in therapeutic options for patients with multiple myeloma (MM), curative outcomes remain elusive. While the introduction of IMIDs, proteasome inhibitors, and antibody-mediated therapies have dramatically improved progression free and overall survival in MM patients, progressive resistance to biologic agents ultimately develops and often results in disease-associated mortality. Novel approaches are needed to improve patient outcomes. Cancer therapeutics has undergone a dramatic change with the observation that cellular

immunotherapy results in sustained disease response in a subset of patients with previously incurable disease. This approach potentially harnesses native immunity to provide specific targeting of tumor cells and the development of memory responses critical to prevent relapse.

## 2.2 Vaccine Therapy for Multiple Myeloma

Immune therapy has emerged as a leading area of cancer therapeutics due to its potential to recruit multiple effectors that broadly target malignant cells and overcome mechanisms of resistance. Multiple myeloma (MM) is characterized by the loss of critical mediators of immune surveillance, resulting in the suppression of antigen-presenting and effector cell function and the development of an immunologic milieu that fosters disease progression. We have developed a tumor vaccine in which patient-derived myeloma cells are fused with autologous dendritic cells (DCs), such that a broad array of myeloma antigens are presented in the context of DC-mediated costimulation. In diverse tumor models that include MM, vaccination of animals with DC/tumor fusions results in protection from an otherwise lethal challenge of malignant cells and, more significantly, eradication of disease in the setting of advanced metastatic involvement. In a phase I study, 17 patients with advanced myeloma (median of 4 prior regimens) underwent vaccination with DC/MM fusions in conjunction with 4 days of GM-CSF administered at the vaccine site. In this study, MM cells were isolated from bone marrow aspirates and fused with autologous DCs generated from adherent mononuclear cells cultured with GM-CSF, IL-4, and TNF $\alpha$ . Vaccine production was successful in all patients and was well-tolerated without evidence of clinically significant autoimmunity. Vaccination resulted in a mean 10-fold expansion of CD4 and CD8 myeloma-specific T cells, as determined by the percentage of cells expressing IFN $\gamma$  in response to *ex-vivo* exposure to autologous tumor lysate. Similarly, vaccination resulted in the development of myeloma-specific antibody responses as documented by SERAX analysis.

## 2.3 Vaccination with DC/Myeloma fusion cells following autologous transplant

Vaccination with DC/Myeloma fusion cells following autologous transplant is associated with potent immune response and conversion from PR to CR in a subset of patients. We completed a clinical trial in which MM patients were vaccinated with DC/MM fusion cells in conjunction with autologous transplantation (ASCT). In the first cohort of the study, twenty-four patients received serial vaccinations following post-transplant hematopoietic recovery. A second cohort of 12 patients received a pre-transplant vaccine followed by post-transplant vaccinations. Vaccine preparation was successful in all patients. Mean yield of the DC and MM cells was  $1.74 \times 10^8$  and  $6.5 \times 10^7$  cells, respectively. Mean fusion efficiency, as determined by the percentage of cells that co-expressed unique DC (CD80, CD86, and/or CD83) and MM (CD38 and/or CD138) antigens, was 38%. The mean dose administered was  $3.6 \times 10^6$  fusion cells. Mean viability of the DC, myeloma, and fusion preparations was 87%, 87%, 79%, respectively. The DC/MM fusion preparations exhibited potent antigen presenting capacity, as evidenced by their stimulation of allogeneic T cell proliferation, with a mean stimulation index of 36.6, similar to that observed with the DC preparation prior to fusion (mean stimulation index of 52.3). In contrast, the unfused myeloma cells demonstrated minimal capacity for T cell stimulation (mean stimulation index of 13.7). All vaccine-associated toxicities were of grade I-II intensity. The most common toxicity was erythema and induration at the vaccine injection site associated with T cell infiltration on biopsy. The other common side effects were transient pruritus, rash, fatigue, fever, and myalgias. One patient had a transiently elevated ANA level without clinical evidence of autoimmunity. One patient developed transient grade 2 leukopenia, but no evidence of graft compromise was observed following vaccination.

Consistent with prior reports, the post-transplant period was associated with the relative suppression of general measures of cellular immunity as manifested by decreased T cell proliferative responses to mitogen or recall antigens. In contrast, the period of post-transplant lymphopoietic reconstitution was associated with the expansion of myeloma-specific T cells that was further boosted following vaccination, as determined by percentage of CD4+ and CD8+ T cells expressing IFN $\gamma$  in response to *ex-vivo* exposure to autologous tumor lysate. In the first cohort that received only post-transplant vaccination, the mean log10-fold increase in myeloma-specific CD4+ T cells from pre-mobilization to post-transplant and from pre-mobilization to peak post-vaccination was 3.55 (95% CI 0.81;15.49) and 10.72 (95% CI 3.89;29.51), respectively. Similarly, the mean log10-fold increase in myeloma-specific CD8+ T cells from pre-mobilization to post-transplant and from pre-mobilization to peak post-vaccination was 6.76 (95% CI 3.02;15.49) and 11.48 (95% CI 4.17;32.36), respectively. A smaller subset of patients underwent a single pre-

transplant vaccination followed by post-transplant boosting. Of note, no difference in peak levels of CD4+ or CD8+ circulating myeloma-specific T cells was observed between the cohort receiving a pre-transplant vaccine and that undergoing post-transplant vaccination alone ( $p=0.185$  and  $p=0.689$ , respectively). For the entire study population, the mean log10-fold increase in myeloma-specific CD4+ T cells from pre-mobilization to post-transplant and from pre-mobilization to peak post-vaccination was 3.55 (95% CI 1.58;8.13) and 9.55 (95% CI 5.37;16.98), respectively. The mean log10 fold increase in myeloma-specific CD8+ T cells from pre-mobilization to post-transplant and from pre-mobilization to peak post-vaccination was 4.37 (95% CI 2.40;7.76) and 8.32 (95% CI 4.68;15.14), respectively. Notably, vaccination was associated with the expansion of T cells targeting the myeloma-specific antigen, MUC1, as determined by tetramer analysis. In a cohort of patients who were HLA-A2, the median percentage of MUC1-specific T cells was 0.12 pre-transplant and increased to 1.84 at 3 months after completion of vaccination ( $p<0.05$ ), representing a median fold increase of 17.5. The expansion of T cells targeting MUC1 in response to vaccination is of particular interest, as we have identified a population of CD34+/MUC1+ cells in the bone marrow of patients with myeloma that demonstrate myeloma-initiating capacity. Seventy-eight percent of patients achieved a CR or VGPR (47% CR/nCR; 31% VGPR). Thirty-one percent achieved a CR/nCR in the early post-transplant period, whereas an additional 17% (6 patients: 4 from VGPR, 2 from PR) achieved CR/nCR as best response only after day 100 post- transplant and after undergoing vaccination. The presence of late responses several months after ASCT is consistent with an impact of vaccine therapy on post-transplant residual disease.

## 2.4 Checkpoint Blockade

A remaining challenge to develop sustained and clinically effective immune therapy for myeloma involves overcoming the immunosuppressive milieu characteristic of the tumor microenvironment. A critical component of this tolerizing environment is the upregulation of negative costimulatory molecules such as programmed death receptor 1 (PD-1) that induced a state of T cell exhaustion. Two ligands specific for PD-1 have been identified: PD-ligand 1 (PD-L1, also known as B7-H1 or CD274, expressed on tumor, antigen-presenting cells [APCs], and dendritic cells [DCs]) and PD-L2 (also known as B7-DC or CD273, expressed on endothelial cells). The interaction of PD-1 with PD-L1 and PD-L2 results in negative regulatory stimuli that down-modulate the activated T-cell immune response through SHP-1 phosphatase. In health, ligation of PD-1 is associated with protection from autoimmune sequelae of immune overstimulation. For example, PD-1 knockout mice develop strain-specific lupus-like glomerulonephritis (C57BL/6) and cardiomyopathy (BALB/c). In the setting of malignancy, upregulation of PD-L1 on tumor cells and ligation of PD-1 on tumor associated lymphocytes results in a state of immune tolerance and escape facilitating tumor growth. In contrast, blockade of the PD-1/PD-L1 pathway has been associated with dramatic and sustained disease responses in a subset of patients with malignancy including malignant melanoma, Hodgkin disease, renal, lung, bladder, and head and neck cancer.

## 2.5 Nivolumab

Nivolumab (BMS-936558, MDX-1106, and ONO-4538) is a fully human monoclonal immunoglobulin G4 (IgG4) antibody (HuMAb) that is specific for human programmed death-1 (PD-1, cluster of differentiation 279 [CD279]) cell surface membrane receptor. PD-1 is a negative regulatory molecule that is expressed transiently following T-cell activation and on chronically stimulated T cells characterized by an “exhausted” phenotype. Nivolumab binds to cynomolgus monkey PD-1 but not mouse, rat, or rabbit molecules. Clinical activity of nivolumab has been observed in patients with melanoma, non-small cell lung cancer (NSCLC), renal cell carcinoma (RCC), and recently in hematologic malignancies. This clinical experience has demonstrated that endogenous immune responses can mediate effective tumor regression and/or improved survival even in patients with large volume tumors resistant to other forms of therapy. It is not yet clear what factors with respect to the tumor cells, their surrounding microenvironment, and the nature of immune dysregulation are determinative of response to the class of checkpoint inhibitors.

### 2.5.1 Nonclinical Development of Nivolumab

In intravenous (IV) repeat-dose toxicology studies in cynomolgus monkeys, nivolumab alone was well tolerated (Investigator Brochure, 2015). Nivolumab bound specifically to PD-1 (and not to related members of the CD28 family such as CD28, ICOS, CTLA-4, and BTLA) with a  $K_d = 3.06$  nM. A surrogate rat anti-mouse PD-1 antibody (4H2) was derived and expressed as chimeric IgG1 murine antibody. Antitumor activity was seen for several tumor

models, including colon carcinoma and fibrosarcoma.

### 2.5.2 Clinical Development of Nivolumab

Nivolumab is being evaluated as monotherapy and in combination with cytotoxic chemotherapy, other immunotherapy (such as ipilimumab), anti-angiogenesis therapy, and targeted therapies in completed and ongoing BMS-sponsored clinical trials in NSCLC, melanoma, RCC, hepatocellular carcinoma (HCC), gastrointestinal (GI) malignancies including microsatellite instability (MSI) in colorectal cancer, and triple-negative breast cancer (TNBC) with an expanding group of indications in hematologic malignancies (Investigator Brochure, 2015). Investigator-sponsored trials (ISTs) of nivolumab in combination with a peptide vaccine in melanoma are being conducted in the adjuvant setting and advanced disease.

### 2.5.3 Pharmacokinetics

Pharmacokinetics (PK) of nivolumab was linear in the range of 0.3 to 10 mg/kg, with dose-proportional increases in maximum serum concentration (Cmax) and area under the concentration-time curve from time zero to infinity (AUC0-∞), with low to moderate inter-subject variability observed at each dose level (Investigator Brochure, 2015). Clearance of nivolumab is independent of dose in the dose range (0.1 to 10 mg/kg) and tumor types studied. Body weight normalized dosing showed approximately constant trough concentrations over a wide range of body weights. The mean terminal elimination half-life of BMS-936558 is 17 to 25 days consistent with the half-life of endogenous IgG4.

### 2.5.4 Efficacy

In a phase 1 (1, 3, and 10 mg/kg nivolumab doses) dose-escalation study, the 3 mg/kg dose was chosen for expanded cohorts. Among 236 patients, objective responses (ORs) (complete or partial responses [CR or PR]) were seen in NSCLC, melanoma, and RCC. ORs were observed at all doses. Median OS was 16.8 months across doses and 20.3 months at the 3 mg/kg dose. Median OS across all dose cohorts was 9.2 months and 9.6 months for squamous and non-squamous NSCLC, respectively. In the RCC cohort, median duration of response was 12.9 months for both doses with 5 of the 10 responses lasting ≥1 year.

### 2.5.5 Toxicology

A maximum tolerated dose (MTD) of nivolumab was not defined. Serious adverse events (SAEs) occurred in 32 of 296 patients (11%) similar to the immune-related inflammatory events seen with ipilimumab: pneumonitis, vitiligo, colitis, hepatitis, hypophysitis, and thyroiditis (with noted pulmonary toxicity resulting in 3 deaths. Renal failure, symptomatic pancreatic and DM, neurologic events, and vasculitis have also been reported.).

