### **5.7 Day 15 of Cycles 1-3 (+/- 3 days)**

1. History, physical examination, height and weight
2. ECOG Performance Status
3. AE Assessment
4. Medications
5. CBC with differential, platelet count
6. Liver Functions and blood chemistries: Na, K, Cl, CO2, Ca, Mg, PO4, Creatinine, total bilirubin, direct bilirubin, alkaline phosphatase, AST, ALT, LDH

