#### **8.1 Expected Toxicities**

##### **8.1.1 Adverse Events Lists**

###### **8.1.1.1 Adverse Event List(s) for Nivolumab**

Events that are listed as very common (experienced in  $\geq 10\%$  of patients) according to the current IB (Version 16 dated June 23, 2017) include the following: fatigue and diarrhea

Events that are listed as common (experienced in  $\geq 1\%$  to  $< 10\%$  of patients) include: hypothyroidism, hyperthyroidism, hyperglycemia, nausea, vomiting, chills, colitis, stomatitis, asthenia, gastritis,

abdominal pain, constipation, dry mouth, pyrexia, edema peripheral, infusion related reactions, increased lipase, increased amylase, increased aspartate aminotransferase, increase alanine aminotransferase, increased creatinine, increased thyroid stimulating hormone, hyponatremia, decreased appetite, back pain, myalgia, arthralgias, pain in extremity, headache, pruritis, dizziness, pneumonitis, dyspnea, cough, rash, vitiligo, dry skin, erythema, maculopapular rash

Events that are listed as uncommon  $\geq 0.001\%$  of patients to  $< 1\%$  include the following: musculoskeletal pain, arthritis, neck pain, musculoskeletal chest pain, bone pain, polyarthritis, peripheral neuropathy, peripheral sensory neuropathy, peripheral motor neuropathy, vasculitis, lung infiltration, tubulointerstitial nephritis, renal failure, acute kidney injury, hypertension, hypotension, alopecia, dermatitis acneiform, macular rash, urticaria, dermatitis, erythematous rash, generalized rash, papular rash, psoriasis, pustular rash, drug eruption, bronchitis, hypersensitivity, upper respiratory infections, edema, facial edema, peripheral swelling, localized edema, nephritis, autoimmune hepatitis, hepatitis, pancreatitis, uveitis, diabetes mellitus, thyroiditis, autoimmune hypophysitis, increased blood bilirubin, hypopituitarism, adrenal insufficiency, tachycardia, autoimmune colitis, atrial fibrillation, vertigo, dry eye, vision blurred, mucosal inflammation, generalized edema, respiratory failure, lung infiltration

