Events that are listed as rare risk (experienced by  $\geq 0.00001\%$  to  $< 0.001\%$  of patients) include arrhythmias, Stevens Johnson Syndrome, dermatitis exfoliative, allergic dermatitis, rosacea, erythema multiforme, diabetic ketoacidosis, autoimmune hypothyroidism, iridocyclitis, periorbital edema, mouth ulceration, acute pancreatitis, acute hepatitis, sarcoidosis, anaphylactic reaction, myositis, musculoskeletal discomfort, osteoarthritis, pain in jaw, polymyalgia rheumatica, polymyositis, rhabdomyolysis, polyneuropathy, burning sensation, encephalitis, Guillain-Barre syndrome, myasthenia gravis, demyelination, autoimmune nephritis, organizing pneumonia, acute respiratory distress syndrome, vasculitis

Events that are listed as very rare (experienced by  $< 0.0001\%$ ) include ventricular arrhythmias, mucosal ulceration, demyelinating polyneuropathy, myasthenic syndrome, and toxic epidermal necrolysis

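### Hyperglycemia and raised lipase and amylase are listed as common nivolumab toxicities, but no scheduled chemistry list measures glucose, lipase or amylase

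*Combined protocol and SAP*

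**What the plan says.** **Toxicities named.** In the common band of section 8.1.1.1 (1% to <10%) the protocol lists "hypothyroidism, hyperthyroidism, hyperglycemia, nausea, vomiting" and, further on, "increased lipase, increased amylase". The uncommon band (below 1%) contains "pancreatitis, uveitis, diabetes mellitus, thyroiditis", and the rare band contains "diabetic ketoacidosis, autoimmune hypothyroidism". No severity grade accompanies any of these frequencies. The background in section 2.5.5 adds that "Renal failure, symptomatic pancreatic and DM, neurologic events, and vasculitis have also been reported".

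**Tests scheduled.** The day 15 visit of cycles 1-3 (section 5.7) gives the chemistry panel as "Liver Functions and blood chemistries: Na, K, Cl, CO2, Ca, Mg, PO4, Creatinine, total bilirubin, direct bilirubin, alkaline phosphatase, AST, ALT, LDH". The same analytes appear in sections 5.1, 5.5, 5.6, 5.9, 5.10, 5.11.1 and 5.11.3. The section 11 calendars refer only to blood chemistries in general.

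**What the data are for.** Section 1.3.2 sets a secondary aim: "To determine the clinical response and safety of nivolumab and the DC/MM fusion vaccine in patients with relapsed disease". Section 8.3.4 excludes a laboratory abnormality from capture when it is both clinically insignificant and unrelated to treatment. Section 7 counts as a TLT a related non-hematologic toxicity of grade 3 or more that is still present after 14 days. Accrual is suspended if 3 or more of the first 10 patients have a TLT in their first 28 days.

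**The concern.** Hyperglycemia and raised pancreatic enzymes are found and graded from a blood result. If a site runs only the listed panel, it has no pre-treatment value and no on-treatment value for them. It also has no dates of onset and resolution, which the 14-day TLT criterion needs. A safety table without these events would then look like a finding when it may only show that the analytes were not on the panel.

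Attribution suffers too. Section 3.3.6 exempts steroids from the 7-day washout, and sections 5.13 and 6.1 allow corticosteroids for adverse events. Without a pre-immunotherapy glucose, a raised value found later cannot be compared with the patient's own starting point. Undetected hyperglycemia is also a matter of patient safety.

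**Working it through.** **1. Listed toxicities against scheduled tests**

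| Toxicity in 8.1.1.1 | Band | Scheduled test in section 5 |
|---|---|---|
| Thyroid disorders | common | TSH, free T4, free T3 |
| Raised AST, ALT | common | AST, ALT |
| Raised creatinine | common | creatinine, creatinine clearance |
| Hyponatremia | common | Na |
| Hyperglycemia | common | none |
| Raised lipase | common | none |
| Raised amylase | common | none |
| Diabetes mellitus, pancreatitis | uncommon | none specific |
| Diabetic ketoacidosis | rare | none specific; CO2 could hint at it |

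The other laboratory toxicities in the table have a matching test. The three that do not are in the same frequency band as those that do, and no reason is given.

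**2. The eight lists.** Sections 5.1, 5.5, 5.6, 5.7, 5.9, 5.10, 5.11.1 and 5.11.3 each contain 14 analytes: Na, K, Cl, CO2, Ca, Mg, PO4, creatinine, total bilirubin, direct bilirubin, alkaline phosphatase, AST, ALT and LDH. The list follows a colon, with no wording that makes it illustrative. The scheduled urine work is for protein and electrophoresis. The calendars name no further analyte.

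**3. The capture rule.** The exclusion in section 8.3.4 needs two conditions together: not clinically significant and not related. A related laboratory abnormality fails the second condition, so it is not excluded. The plan thus asks for these events to be captured without scheduling the tests that would show them.

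**4. How many events are in question (any grade).** Inputs: the 1% to <10% band (8.1.1.1) and n = 25 (14.1). Since the band excludes 10%, the upper figures are ceilings.

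- Expected patients per listed toxicity: 25 × 0.01 = 0.25 to 25 × 0.10 = 2.5.
- Probability of at least one: 1 − 0.99^25 = 0.222 to 1 − 0.90^25 = 0.928.
- If none is recorded, the one-sided 95% upper limit for 0 of 25 is 1 − 0.05^(1/25) = 0.113.

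**5. The TLT rule.** The plan's own table comes first. With X binomial (10, p), enrollment continues if X ≤ 2. At p = 0.25: 0.75^10 + 10(0.25)(0.75^9) + 45(0.25²)(0.75^8) = 0.0563 + 0.1877 + 0.2816 = 0.5256, against 0.526 in section 14.1. The entries at 0.10, 0.20, 0.30 and 0.40 recompute to 0.9298, 0.6778, 0.3828 and 0.1673, so all five match.

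The table assumes that every TLT is observed. Let u be the share of patients whose only TLT is one of these abnormalities and is never measured. The observed rate is then p − u. The documents give no value for u. The range below is an assumption, and its top is the any-grade band limit, hence a ceiling.

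| True TLT rate | u = 0 | 1% | 2% | 5% | 10% |
|---|---|---|---|---|---|
| 0.25 | 0.526 | 0.556 | 0.586 | 0.678 | 0.820 |
| 0.30 | 0.383 | 0.410 | 0.438 | 0.526 | 0.678 |
| 0.40 | 0.167 | 0.184 | 0.202 | 0.262 | 0.383 |

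The direction is certain: any missed TLT makes continuation more likely than tabulated. The amount is not known.

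**The case against.** The case for leaving the plan alone has real weight.

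- **Detection is not ruled out.** A reader might infer that these events cannot be detected at all. The documents do not support that. The lists set scheduled tests and forbid no others, CO2 is on the panel, and history, examination and AE assessment occur at every treatment visit. The GI and endocrine algorithms in Appendix B are figures that could not be seen and may call for further tests. What stands is that no listed scheduled test measures these analytes. Ad hoc testing also gives no common denominator.
- **The background sentence concerns symptomatic disease.** Section 2.5.5 does not establish silent events; the laboratory point rests on section 8.1.1.1.
- **The TLT effect is narrow.** A reader might infer that the stopping rule is broadly compromised. Section 6.1 keeps clinically insignificant laboratory findings out of the holding criteria, section 7 limits grade 4 non-hematologic TLTs to clinically significant ones, and a footnote in Appendix B makes a similar exemption. These largely set aside an isolated enzyme rise. What remains is mainly silent, persistent hyperglycemia of grade 3 or higher.
- **The 22% to 93% range is not a TLT probability.** It covers any grade. Section 14 plans no event-specific AE rate or interval either, so 0 of 25 with an 11.3% limit is an illustration and not a planned output.
- **An expected-AE list is not a promise to screen for every item.** That is fair, and which tests to schedule is for the sponsor. It does not explain how section 8.3.4 can be met for these three.
- **A baseline would not separate nivolumab from steroids in a single-arm trial.** Agreed; it would only identify pre-existing elevation.

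**Conclusion.** The point holds as a mismatch between the protocol's list of nivolumab toxicities and its scheduled chemistry. Three toxicities that it calls common have no listed scheduled test and no scheduled baseline, so their absence from the safety results could not be told apart from lack of measurement. For each, 0.25 to 2.5 affected patients of any grade would be expected among 25, if the listed band applies to this population.

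For the TLT rule, only the direction of the error can be stated. The sensitivity table rests on an assumed share of missed TLTs, and the any-grade frequencies cannot supply that share. The conclusion also assumes that sites run the panel as written and that the unseen Appendix B figures add no routine test. It merits correction because it touches a stated endpoint and patient safety. It does not show that the TLT rule fails.

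**What to change.** Reconcile the chemistry lists in sections 5.1, 5.5, 5.6, 5.7, 5.9, 5.10, 5.11.1 and 5.11.3 with section 8.1.1.1, in one of two ways:

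1. Cover the listed laboratory toxicities in the scheduled chemistry, using blood already drawn. Which analytes and which visits is for the sponsor to decide.
2. State in sections 1.3.2 and 7 that these laboratory toxicities are not systematically ascertained, and report no incidence for them.

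If the Appendix B algorithms already call for such tests, a cross-reference should say when they apply and whether the results enter the study data.

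Cost: the first option needs no new visit or procedure and brings a few more low-grade laboratory events to record. The second needs a short statement in each of the two sections and leaves a narrower safety claim.
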